## 10. Tender/Painful Joint Count (68)

Tender/painful joints are recorded in the CRF page of joint tender/painful. For each of the 68 joints, tender/painful can be recorded as "Present", "Absent", "Not Done", "Not Applicable" or this joint assessment is simply missing. The tender/painful joint count will be calculated per Pfizer's standard similarly as for the swollen joint count (see Appendix 3 Section 9).

## 11. Leeds Enthesitis Index (LEI) and Resolution of Enthesitis

Six sites, including (right and left): lateral\_epicondyle humerus, medial femoral condyle and Achilles tendon insertion, are assessed for enthesitis. Leeds Enthesitis Index (LEI) is the number of sites with presence of enthesitis.

Each of the 6 sites is assessed as "Present", "Absent", "Not Done", "Not Applicable" or simply missing. Before calculating the LEI, the pre-processing steps for each site will be performed per Pfizer's standard as follows.

- A site recorded as "Not Done" is set to missing.
- A site recorded as "Not Applicable" means that measurement cannot be made and this site is set to missing.

After this pre-processing, a site assessment that is set to missing is to be imputed by the average of the non-missing values of the other sites, with the restriction that the number of missing site assessments cannot exceed 50% of the expected total number of sites evaluated for the LEI (i.e., 3, 50% of 6). In that case, the LEI is set to missing.

Explicitly after pre-processing, let

• N1=number of sites recorded as "Present";

- N2=number of sites recorded as "Absent";
- N3=number of sites with missing values.

The total number of sites assessed is  $N=N_1+N_2+N_3$  (i.e., 6). The calculated LEI is therefore  $N_1+N_3\times(N_1/(N_1+N_2))$  if  $N_1+N_2>3$ ; otherwise the LEI is set to missing. The calculated LEI will be rounded to a whole number. For example, a value of 4.5 is rounded to 5, a value of 4.49 is rounded to 4. Note that if there is no missing site assessment, the LEI will be the number of sites recorded as "Present" (i.e.,  $N_1$ ).

Resolution of enthesitis is defined as a subject with LEI=0.

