#### 5.3. Methods to Manage Missing Data

As stated in the protocol, in the primary analysis of the primary endpoint, ACR50 response rate at Month 3, missing values for any reason, e.g., due to a subject dropping from the study or due to the impact of COVID-19 pandemic, will be handled by setting the ACR50 value to nonresponsive. Note that this can be viewed as a composite endpoint in the sense that a response requires the subject completes a visit of interest, e.g., Month 3, and achieves a response per the defined ACR50 response criteria (otherwise it is considered a nonresponse). This method of handling missing response is known as missing response as non-response (MR=NR). This MR=NR approach will be used for all "response-type" endpoints at all timepoints except for the supportive analyses using GMMRM (see Section 5.2.1.2) and Tipping Point Analysis (see Section 5.2.1.3) for ACR50 up to Month 3. Note that if a subject

discontinues from the study at a visit of interest, say Month 3, but the value of the endpoint is not missing at Month 3, the value of the endpoint will be used for Month 3.

For a composite "response-type" endpoints (such as ACR50), if values in any of the components at a timepoint are missing, the component variables that are not missing will be used to determine the response status. If one could not determine the response status in the presence of missing components at the timepoint, then the composite response-type endpoint status is considered as missing and is handled by MR=NR for that timepoint for all of the inferential analyses except for the supportive analyses using GMMRM (see Section 5.2.1.2) and Tipping Point Analysis (see Section 5.2.1.3) for ACR50 up to Month 3.

Repeated measures data for continuous and ordered-categorical (analyzed as continuous) endpoints will be analyzed with MMRM. This model will yield unbiased estimates and valid inferences in the presence of data that is MCAR or missing at random (MAR). Given that subjects who drop out are scheduled to have an end of study evaluation, the more stringent condition of MAR (Rubin, 1987) is believed to be a reasonable assumption. Hence missing values will not be imputed in the routine analysis using the repeated measures model.

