#### **Endpoint:** Resolution of enthesitis (achieving LEI = 0)

- Analysis time points: Month 1, Month 3, Month 6
- $\circ$  Analysis population: Subjects in FAS with baseline LEI > 0

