## 9. Swollen Joint Count (66)

Swollen joints are recorded in the CRF page of joint swelling. For each of the 66 joints, swelling can be recorded as "Present", "Absent", "Not Done", "Not Applicable" or this joint assessment is simply missing. Before calculating the swollen joint count, the following pre-processing steps for each joint should be performed per Pfizer's standard:

- If a joint receives an intra-articular injection (either at Baseline or post-baseline visits), set the joint status to "Present" on or after the date of injection regardless of the assessment of the joint recorded on the CRF page.
- If there is no associated injection record available, a joint recorded as "Not Done" is set to missing.
- A joint recorded as "Not Applicable" means that measurement cannot be made and this joint is set to missing.

After this pre-processing, a joint assessment that is set to missing is to be imputed by the average of the non-missing values of the other joints, with the restriction that the number of missing joint assessments cannot exceed 50% of the expected total number of joints evaluated for the swollen joint count (i.e., 33, 50% of 66). In that case, the swollen joint count is set to missing.

Explicitly after pre-processing, let

- N1=number of joints recorded as "Present";
- N2=number of joints recorded as "Absent";
- N3=number of joints with missing values.

The total number of joints assessed is  $N_1 + N_2 + N_3$  (i.e., 66). The calculated swollen joint count is therefore  $N_1 + N_3 \times (N_1/(N_1 + N_2))$  if  $N_1 + N_2 > 33$ ; otherwise the swollen joint count is set to missing. The calculated swollen joint count will be rounded to a whole number. For example, a value of 24.5 is rounded to 25, a value of 24.49 is rounded to 24. Note that if there is no missing joint assessment, the swollen joint count will be the number of joints recorded as "Present" (i.e.,  $N_1$ ).

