## 12. Dactylitis Severity Score (DSS) and Resolution of Dactylitis

Each of the 20 digits in hands and feet with dactylitis will be evaluated. Dactylitis severity will be scored based upon digit tenderness using a scale of 0-3, (0-NONE, 1-MILD, 2-MODERATE, 3-SEVERE, 8-NOT APPLICABLE, 9-NOT DONE), in each digit of the hands and feet. Dactylitis severity score (DSS) is the sum of the severity scores of the 20 digits (range: 0-60, with a higher score indicating more severe dactylitis).

Before calculating the DSS, the pre-processing steps for each digit will be performed per Pfizer's standard as follows.

- A digit recorded as "Not Done" is set to missing.
- A digit recorded as "Not Applicable" means that measurement cannot be made and this digit is set to missing.

Let N1 be the number of digits with missing values, and N2 and S be the number of the digits and the sum of the digit scores assessed as 0-NONE, 1-MILD, 2-MODERATE, OR 3-SEVERE, respectively, the calculated DSS is:  $S + N_1 \times \frac{S}{N_2}$ , if N1<N2; otherwise the DSS is set as missing.

The calculated DSS is rounded to the whole number. For example, a value of 24.5 is rounded to 25, a value of 24.49 is rounded to 24.

Resolution of dactylitis is defined as a subject with DSS=0.

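### Enthesitis or dactylitis can be scored as resolved when the sites or digits affected at baseline were not examined

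*SAP*

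**What the plan says.** SAP Appendix 3 Section 11 builds the Leeds Enthesitis Index (LEI) from six sites. A site recorded Not Done or Not Applicable is first set to missing, and then "a site assessment that is set to missing is to be imputed by the average of the non-missing values of the other sites". The fill is allowed "with the restriction that the number of missing site assessments cannot exceed 50% of the expected total number of sites evaluated for the LEI", given there as 3 of 6. The formula that follows applies only if more than three sites were scored.

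Section 12 treats the 20 digits of the Dactylitis Severity Score (DSS) in the same way. The sum over scored digits is scaled up if fewer digits are missing than scored; "otherwise the DSS is set as missing".

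The binary endpoints are taken from these scores: "Resolution of enthesitis is defined as a subject with LEI=0", and "Resolution of dactylitis is defined as a subject with DSS=0". SAP 6.2.1 analyses enthesitis resolution in "Subjects in FAS with baseline LEI > 0", and dactylitis resolution in the matching DSS subset, at Months 1, 3 and 6. Missing responses count as non-response (MR=NR).

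For a composite endpoint, SAP 5.3 applies MR=NR under the condition "If one could not determine the response status in the presence of missing components at the timepoint". SAP 5.1 calls p-values for all endpoints other than Month 3 ACR50 nominal.

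Section 9 has the parallel rule for the swollen joint count, where "a joint assessment that is set to missing is to be imputed by the average of the non-missing values of the other joints". Section 10 adopts it for the tender joint count.

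**The concern.** The resolution endpoints ask whether disease present at baseline has gone. Their analysis sets contain only subjects with at least one affected site or digit, so the state of those places decides the outcome. The fill rule does not use an item's baseline status. If the examined items are clear, an unexamined item is scored as clear, even if it is the one that brought the subject into the analysis set.

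A subject can then be reported as resolved with no observation of the affected place. Partial examinations are foreseeable: Not Done is a recording option for every site and digit, and Protocol Section 7.7 expects partly completed assessments under COVID-19 restrictions.

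**Working it through.** The plan gives no figure for these endpoints. Its power statement (Protocol 9.1) concerns ACR50 only and plays no part here. The check puts cases through the SAP formulas.

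**LEI (Appendix 3 Section 11).** With N1 sites Present, N2 Absent and N3 missing, LEI = N1 + N3 × N1/(N1+N2), if N1+N2 > 3.

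- Baseline LEI 1; that site Not Done, the other five Absent: 0 + 1 × 0/5 = 0, scored as resolved.
- Baseline LEI 2; both sites Not Done, the other four Absent: N1+N2 = 4 > 3, and 0 + 2 × 0/4 = 0, scored as resolved.
- Three sites Not Done, the other three Absent: N1+N2 = 3, so the formula makes LEI missing and MR=NR gives non-response. By the words, 3 does not exceed 50% of 6, so the fill is allowed: 0 + 3 × 0/3 = 0, scored as resolved. Here the mismatch changes the outcome.

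**DSS (Appendix 3 Section 12).** Here N1 is the number of missing digits, N2 the number scored and S the sum of scores. DSS = S + N1 × S/N2, if N1 < N2.

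- Nine digits Not Done, the other eleven clear: 9 < 11, and 0 + 9 × 0/11 = 0, scored as resolved.
- Ten Not Done: 10 < 10 is false, so DSS is missing and MR=NR gives non-response.

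**Direction for the two resolution endpoints.** If any examined site is Present, N1 ≥ 1 and LEI ≥ 1. The subject is unresolved, and rightly so whatever the unexamined sites hold. If no examined site is Present, the filled LEI is 0 whatever they hold. The fill can therefore turn an unresolved subject into a resolved one, never the reverse. The same holds for DSS with S ≥ 1 or S = 0.

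**Whether anything later catches it.** MR=NR acts on a missing status, and a filled score of 0 is not missing. The supportive analyses in SAP 6.1.1.2 and 6.7.1 all concern ACR50. None varies the item-level rule.

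**Weight of one misclassified subject.** Planned arms are 136 and 68 (Protocol 9.1). The share of subjects with baseline LEI > 0 or DSS > 0 is not given, so the shares below are assumptions.

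| Assumed share affected | Placebo | Tofacitinib |
|---|---|---|
| One quarter | 1/17 = 5.9 points | 1/34 = 2.9 points |
| One half | 1/34 = 2.9 points | 1/68 = 1.5 points |
| All | 1/68 = 1.5 points | 1/136 = 0.7 points |

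These are weights per subject, not estimates of bias. The number of such subjects is unknown.

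**The 50% limit for joints (Section 9).** With 33 of 66 joints missing, the words allow the fill, because 33 does not exceed 50%. The formula needs N1+N2 > 33 and sets the count to missing. Section 10 inherits this; half of 68 is 34. Section 12 states only a formula, so it has no mismatch.

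**The case against.** The best defence is that scoring from available items is the SAP's general practice. HAQ-DI averages the non-missing domains, SF-36 scales substitute the mean of the answered items, and the LEI, DSS and joint rules are described as company standard. The endpoints are secondary, assessors are blinded, and the missing data that SAP 5.3 names arise from dropout and COVID-19. A wholly missed examination leaves the score missing, and MR=NR then applies.

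Much of this stands. The problem may be rare, nothing suggests that it differs by arm, and averaging is a reasonable rule for a continuous score. It does not rescue the resolution endpoints. They are all-or-none statements about places known to be affected, and an average over other places says nothing about those.

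Three stronger readings are tempting, and the documents do not support them.

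- *That Appendix 3 contradicts SAP 5.3.* It does not. Section 5.3 deals with derived components that are missing, while Appendix 3 works one level lower and decides when a score is missing. The non-response rule is bypassed, not contradicted.
- *That non-response is the principle everywhere else.* The HAQ-DI and SF-36 rules show otherwise.
- *That the error always favours response and so inflates ACR50.* For joint counts it runs both ways. With baseline 6, three affected joints Not Done, three still swollen and 60 Absent, the count is 3 + 3 × 3/63 = 3.14, rounded to 3, a 50% improvement. With baseline 20, ten swollen, 52 Absent and four never-affected joints Not Done, it is 10 + 4 × 10/62 = 10.65, rounded to 11, a 45% improvement, so a subject with a true 50% improvement fails. ACR50 also needs the tender count and three of five other measures to improve by 50%, so this route is remote.

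**Conclusion.** The point holds for resolution of enthesitis and resolution of dactylitis. As written, the SAP scores a subject as resolved when the affected sites or digits were not examined and the examined ones are clear, within 2 of 6 sites or 9 of 20 digits by the formulas. This follows from the formulas and needs no assumption. An LEI subject with three or more affected sites cannot be called resolved with all of them unexamined, because the formula then makes the score missing.

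The size is unknown, because no frequency of Not Done items is given. A reader might infer a bias in favour of tofacitinib. The documents do not support that: the rule can raise the resolution rate in either arm, and nothing indicates unequal missingness. The consequence is possible misclassification in two secondary endpoints with nominal p-values. The primary analysis is not called into question.

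The mismatch between words and formula at exactly half missing is certain, and should be corrected whatever view is taken of the averaging.

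**What to change.** 1. **Appendix 3 Sections 11 and 12, resolution endpoints only.** Add: if any site or digit that was positive at baseline is Not Done or otherwise missing at the visit, and all examined ones are clear, resolution status is missing and MR=NR applies. If any examined site or digit is still positive, the subject is unresolved, as now.
2. **Leave the averaging rule unchanged** for continuous LEI and DSS and for the joint counts. Carrying baseline status into these scores is not advised: it would enter the change scores analysed by MMRM and the DAS28-3(CRP), and pull them towards no change.
3. **Make the 50% limit agree in Sections 9 and 11, and in Section 10 by reference.** One way is to require in the text that missing items be less than 50%, which matches the formulas (more than 33 joints or 3 sites scored). State the tender-count limit explicitly, as more than 34 of 68.

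The cost is SAP wording and a small derivation change on item-level data already collected. Resolution rates may fall slightly in both arms. A few subjects will have a filled LEI or DSS of 0 in the continuous analysis but a missing resolution status, and will leave the denominator of the unimputed summaries (SAP 5.2). A sentence in the SAP should say that this is intended.

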## 12. Dactylitis Severity Score (DSS) and Resolution of Dactylitis

Each of the 20 digits in hands and feet with dactylitis will be evaluated. Dactylitis severity will be scored based upon digit tenderness using a scale of 0-3, (0-NONE, 1-MILD, 2-MODERATE, 3-SEVERE, 8-NOT APPLICABLE, 9-NOT DONE), in each digit of the hands and feet. Dactylitis severity score (DSS) is the sum of the severity scores of the 20 digits (range: 0-60, with a higher score indicating more severe dactylitis).

Before calculating the DSS, the pre-processing steps for each digit will be performed per Pfizer's standard as follows.

- A digit recorded as "Not Done" is set to missing.
- A digit recorded as "Not Applicable" means that measurement cannot be made and this digit is set to missing.

Let N1 be the number of digits with missing values, and N2 and S be the number of the digits and the sum of the digit scores assessed as 0-NONE, 1-MILD, 2-MODERATE, OR 3-SEVERE, respectively, the calculated DSS is:  $S + N_1 \times \frac{S}{N_2}$ , if N1<N2; otherwise the DSS is set as missing.

The calculated DSS is rounded to the whole number. For example, a value of 24.5 is rounded to 25, a value of 24.49 is rounded to 24.

Resolution of dactylitis is defined as a subject with DSS=0.

## 13. AEs of Special Interest

- Serious infections (SIs)
- Herpes zoster (HZ)
- Adjudicated opportunistic infections (OIs) excluding tuberculosis (TB)a
- Hematologic events (anaemia, neutropenia, lymphopenia, and thrombocytopenia)
- Adjudicated malignanciesa
- Adjudicated major adverse cardiovascular events (MACE)a,b
- Adjudicated deep vein thrombosis (DVT)a
- Adjudicated pulmonary embolism (PE)a
- Adjudicated venous thromboembolism (VTE)a (i.e., adjudicated DVTa or adjudicated PEa)
- Arterial thromboembolism (ATE)c
- Thromboembolism (TE) (i.e., adjudicated DVTa, adjudicated PEa, or ATEc)
- Adjudicated drug-induced liver injury (DILI)a and other hepatic eventsd
- Renal eventse
- Adjudicated gastrointestinal (GI) perforationsa
- Adjudicated interstitial lung disease (ILD)f

Abbreviations: CMQ = Customized MedDRA Queries; DILI = drug-induced liver injury;

GI = gastrointestinal; HZ = herpes zoster; ILD = interstitial lung disease; MACE = major adverse

cardiovascular events; MedDRA = Medical Dictionary for Regulatory Activities; OI = opportunistic

infection; SI = serious infection; SMQ = Standardised MedDRA Queries; TB = tuberculosis.

a. Adjudicated by Adjudication Committees independent and external to Pfizer.

b. Components: cardiovascular death, non-fatal myocardial infarction, and non-fatal stroke.

c. CMQs to be included will be specified in the programming plan.

d. Including SMQs: Hepatic failure, fibrosis, and cirrhosis, and other liver damage-related conditions; and Hepatitis, non-infectious.

e. Including acute renal failure SMQ.

f. Adjudicated by an internal review committee.

# 14. Definition of Diabetes Mellitus at Baseline

A subject is considered having diabetes mellitus at baseline, if any of the conditions below is met:

- subject had a diagnosis of diabetes mellitus recorded on the "SIGNIFICANT MEDICAL HISTORY" CRF at screening,
- subject received any drug treatment taken on Day 1 recorded on the "PRIOR AND CONCOMITANT MEDICATIONS: OTHER" CRF in the "ANTI-DIABETIC AGENTS" category,
- subject's HbA1c  $\ge$  6.5% at baseline or, if HbA1c is not available, baseline fasting plasma glucose  $\ge$  126 mg/dL.

## 15. Criteria for Clinical Diagnosis of the Metabolic Syndrome

Criteria for clinical diagnosis of the metabolic syndrome will be based on the 2009 Joint Statement Harmonizing the Metabolic Syndrome (Alberti et al, 2009). There are 5 measures or risk factors as detailed in Table 1 of the 2009 Joint statement and excerpted below:

Measure	Categorical Cut Points	
Elevated waist circumference*	Population- and country-specific definitions	
Elevated triglycerides (drug treatment for elevated triglycerides is an alternate indicator†)	$\geq$ 150 mg/dL (1.7 mmol/L)	
Reduced HDL-C (drug treatment for reduced HDL-C is an alternate indicator†)	<40 mg/dL (1.0 mmol/L) in males; <50 mg/dL (1.3 mmol/L) in females	
Elevated blood pressure (antihypertensive drug treatment in a patient with a history of hypertension is an alternate indicator)	Systolic $\geq$ 130 and/or diastolic $\geq$ 85 mm Hg	
Elevated fasting glucose‡ (drug treatment of elevated glucose is an alternate indicator)	$\geq$ 100 mg/dL	

HDL-C indicates high-density lipoprotein cholesterol.

\*It is recommended that the IDF cut points be used for non-Europeans and either the IDF or AHA/NHLBI cut points used for people of European origin until more data are available.

†The most commonly used drugs for elevated triglycerides and reduced HDL-C are fibrates and nicotinic acid. A patient taking 1 of these drugs can be presumed to have high triglycerides and low HDL-C. High-dose  $\omega$ -3 fatty acids presumes high triglycerides.

‡Most patients with type 2 diabetes mellitus will have the metabolic syndrome by the proposed criteria.

Any 3 abnormal findings out of the 5 measures will qualify a subject for the metabolic syndrome.

The baseline (i.e., Day 1) data will be used to derive the metabolic syndrome.

- Any drug treatment taken on Day 1 recorded on the "PRIOR AND CONCOMITANT MEDICATIONS: OTHER" CRF in the "ANTI-DIABETIC AGENTS" category will be considered having the drug treatment of elevated glucose criterion satisfied.
- Any drug treatment taken on Day 1 recorded on the "PRIOR AND CONCOMITANT MEDICATIONS: OTHER" CRF in the "ANTI-HYPERTENSION AGENTS"

category will be considered having the drug treatment of elevated blood pressure criterion satisfied.

- Any drug treatment taken on Day 1 recorded on the "PRIOR AND CONCOMITANT MEDICATIONS: OTHER" CRF in the "LIPID LOWERING AGENTS" category will be considered having the drug treatment of elevated triglycerides criterion satisfied.
- For the HDL-C criterion, only the lab categorical cut-points will be considered and the drug treatment will not be considered.
- The waist circumference thresholds will be population and country specific per Table 2 of the 2009 Joint Statement excerpted below. Explicitly, the China specific threshold will be used for this China-alone study.

		Recommended Waist Circumference Threshold for Abdominal Obesity	
Population	Organization (Reference)	Men	Women
Europid	IDF (4)	≥94 cm	≥80 cm
Caucasian	WHO (7)	$\geq$ 94 cm (increased risk)	$\geq$ 80 cm (increased risk)
		$\geq$ 102 cm (still higher risk)	$\geq$ 88 cm (still higher risk)
United States	AHA/NHLBI (ATP III)* (5)	≥102 cm	≥88 cm
Canada	Health Canada (8,9)	≥102 cm	≥88 cm
European	European Cardiovascular Societies (10)	≥102 cm	≥88 cm
Asian (including Japanese)	IDF (4)	≥90 cm	≥80 cm
Asian	WHO (11)	≥90 cm	≥80 cm
Japanese	Japanese Obesity Society (12)	≥85 cm	≥90 cm
China	Cooperative Task Force (13)	≥85 cm	≥80 cm
Middle East, Mediterranean	IDF (4)	≥94 cm	≥80 cm
Sub-Saharan African	IDF (4)	≥94 cm	≥80 cm
Ethnic Central and South American	IDF (4)	≥90 cm	≥80 cm

